[name], PhD
Professor of Laboratory Medicine
University of Washington
Member, Vaccine & Infectious Disease Division
Fred Hutchinson Cancer Research Center
[name]
[name]
[contact]
E-mail: [contact]

[name]
Research Professor of Laboratory Medicine
University of Washington
Joint Associate Member, Vaccine & Infectious Disease Division
Virology Research Clinic
Harborview Medical Center
[name]
[contact]
E-mail: [contact]

[name]
Professor of Pharmacy
Department of Population Sciences
City of Hope
Beckman Research Institute
[name]
[name]
[contact]
Email: [contact]

Clinical Protocol

List of Abbreviations

AE	Adverse Event/Adverse Experience
ART	Antiretroviral Therapy
ca-DNA	Cell-associated HIV DNA
ca-RNA	Cell-associated HIV RNA
CFR	Code of Federal Regulations
CMV	Cytomegalovirus
CRF	Case Report Form
dd-PCR	Digital droplet PCR
DSMB	Data and Safety Monitoring Board
FDA	Food and Drug Administration
GCP	Good Clinical Practice
HIPAA	Health Insurance Portability and Accountability Act
HIV	Human Immunodeficiency Virus
IND	Investigational New Drug
IEC	Independent or Institutional Ethics Committee
IMPDH	Inosine Monophosphate Dehydrogenase Activity
IRB	Institutional Review Board
IUPM	Infectious Unit Per Million
MMF	Mycophenolate Mofetil
N	Number (typically refers to participants)
NIAID	National Institute of Allergy and Infectious Diseases, NIH
NIH	National Institutes of Health
OHRP	Office for Human Research Protections
OHSR	Office for Human Subjects Research
PBMC	Peripheral Blood Mononuclear Cells
PI	Protease Inhibitor
PK	Pharmacokinetics
PO	Per os (by mouth)
QVOA	Quantitative Viral Outgrowth Assay
SAE	Serious Adverse Event/Serious Adverse Experience
scVL	Single copy plasma viral load
TAPT	Total Anti-Proliferation Test
TILDA	Tat/rev-Induced Limiting Dilution Assay
TREC	T Cell Receptor Excision Circles
VL	Viral Load
WHO	World Health Organization

Clinical Protocol

Protocol Summary

[figure not shown]
Table 1. Summary of Protocol	
Full Title	Mycophenolate mofetil therapy for reduction of the HIV reservoir
Short Title	MMF for HIV reservoir reduction
Clinical Trial Phase	Phase II study
IND Sponsor (if applicable)	Applied and confirmed “exempt” status with FDA
Conducted By	Fred Hutchinson Cancer Research Center University of Washington
Principal Investigators	[name], MSc and [name], PhD
Sample Size	Approximately 5 HIV-infected subjects
Study Population	HIV infected individuals on ≥2 years of suppressive ART who will specifically need to have demonstrated full viral suppression with at least four negative plasma viral loads with no more than one documented viral blip during this time.
Study Site	University of Washington AIDS Clinical Trials Unit (UW ACTU) at Harborview Medical Center in Seattle
Study Design	A prospective, open label trial
Study Duration	Accrual will require approximately 2 months. Each enrolled participant will be followed for 22 months
Study Agent	Mycophenolate mofetil or Myfortic©
Treatment Duration	22 months
Primary Objective	Establish the impact of prolonged anti-proliferative therapy on the HIV reservoir. We will test the following hypotheses: 
1. MMF or Myfortic© therapy will lead to a progressive decrease in reservoir size over 22 months of treatment.2. MMF or Myfortic© therapy will lead to a continual shift in HIV reservoir composition from primarily effector memory CD4+ T cells (T_{em}) and central memory CD4+ T cells (T_{cm}) to primarily stem cell like memory (T_{scm}) and naïve (T_n) CD4+ T cells.3. MMF or Myfortic© will eliminate detectable measures of the HIV reservoir, including by cell-associated DNA/mRNA and quantitative viral outgrowth.
Secondary Objectives	Establish the safety of prolonged MMF or Myfortic© therapy in 5 chronically HIV-1 infected patients whose viral loads are fully suppressed by ART.

Clinical Protocol

	
We will test the following hypotheses:
 
1. MMF or Myfortic© will be well-tolerated and will not decrease adherence to or antiviral efficacy of ART.2. Peripheral CD4+ T cell counts and percentages will not meaningfully decrease during treatment with MMF or Myfortic© and ART.3. There will be no excess risk of opportunistic infections in MMF or Myfortic© treated study participants.
Endpoint	The primary endpoint of the study is HIV reservoir size at the end of drug treatment.

Clinical Protocol

Figure 1: Study schema

Clinical Protocol

Table 2. Schedule of study visits and blood draws

ACTU-2100 MMF Study Schedule of Events						
VERSION 6						
TEST/TIMING	Eligibility	Entry	MMF 500mg QD LEAD-IN / STEP 1			IF NO ANTI-PROLIFERATIVE EFFECT, MMF 750mg BID LEAD-IN / STEP 2b
			week 1	week 2 T	week 2 P	
2018 Flu Vaccine month 6~12						
Flu vaccine response evaluation						
Rectal Biopsies OPTIONAL (to [name] Lab)			BIOP			
Complete Interview/Complete PE	X					
Limited Interview/Limited PE		X	X	X		
Limited Interview only (no PE)						
Discussion of MMF side effects	X	X				
Obtaining consent	X					
MMF Drug 500mg MMF for the first week, then go up to 2x500mg for the second week			Dispense x1 week	Dispense x2 weeks		Dispense x2 wks or x5 wks
Urine PG---all visits with safety labs	0	0	0	0		0
PT/PTT (Pre-BIOP safety) blue	4.5					
CBC & Diff Lavender Hemogard Tube)	3	3	3	3		3
Comp Panel (3.5mL SST)	3.5	3.5	3.5	3.5		3.5
CD4/CD8 (Lavender Top Tube)	4	4	4	4		4
MMF Levels (at HMC) (3.5mL SST)		3.5		3.5	3.5	
HCABX & HBSAGX (only-as needed) (5mL SST)	5					
TB IGRA (only-as needed) (3 Quantiferon-TB Gold Tubes 1 mL each	3					
Low Level VL Assay (10mL EDTA)		0				20
QVOA		100				
Anti-Proliferation Assay (3.5mL SST)		7		3.5	3.5	
8.5mL Yellow ACD tubes for Anti Proliferation Assays, FACS for Ki67, TREC level PCR, Cell-associated DNA and mRNA ddPCR, PBMC and plasma banking			85	8.5	8.5	
2.5 mL PAXgene Blood RNA Tube for [name] Lab		5		5		2.5
MLs	23	211	10.5	31	15.5	142
Rolling volumes/8 weeks (max 450mL)		234.0	244.5	275.5	291.0	291
TEAspoons	4.7	42.8	2.1	6.3	3.1	433.0
TABLEspoons	1.6	14.3	0.7	2.1	1.0	448.5
						0.0
						28.8
						3.1
						0.0
						9.6
						1.0
Eligibility	Entry	week 1	week 2 T	week 2 P	week 3	week 4 T
						week 4 P

Phone call to stop MMF in case of lacking efficacy by anti-proliferation test

Clinical Protocol

BIOP						
week 60	wk 74 T	wk 74 P	wk 88 T	wk 88 P	week 90	
Mo. 15	Mo. 18.5	Mo. 18.5	Mo. 22	Mo. 22	Mo. 22.5	ConVF
						PreDC
X	X		X			X
R	R					
0	0		0		0	0
3	3		3		3	3
3.5	3.5		3.5		3.5	3.5
4	4		4		4	4
3.5	3.5	3.5	3.5	3.5	3.5	
20	20		0		20	20
			100			
3.5	3.5	3.5	3.5	3.5		
212.5	212.5	8.5	119	8.5		
5	5		5			
255	255	15.5	241.5	15.5	14	20
255.0	255.0	270.5	241.5	257.0	271.0	
51.7	51.7	3.1	49.0	3.1	2.8	4.1
17.2	17.2	1.0	16.3	1.0	0.9	1.4
week 60	week 74	week 74	week 88	week 88	week 90	

The bottom row in red indicates rolling blood volumes over 8 weeks prior to and including each blood draw and should not be higher than a total of 450 mL as per University of Washington policy.

Clinical Protocol

1.0 INTRODUCTION

1.1 Background

The use of antiretroviral therapy (ART) in HIV-infected patients is a shining success in medicine. These medications allow millions of patients to survive for decades, whereas untreated infection is often fatal within ten years. Widespread implementation of ART has also decreased HIV transmission because aviremic infected persons have little to no transmission potential.¹ Nevertheless, there is still an urgent need for an HIV cure that would eliminate all of the virus from the body. Complete HIV eradication, or at least a functional cure in which too little HIV remains for the virus to reactivate over the lifespan of the infected person, would allow infected persons to permanently stop taking anti-viral therapy. An immediate benefit of cure would be avoidance of possible ART-associated toxicities and drug interactions.^{1,2} A definitive cure of HIV would reduce the stigma felt by many infected persons.³ Finally, the transformation of HIV care provision from a chronic model whereby ART is given over decades to a cure therapy given over a few years, would save the United States healthcare system massive healthcare expenditures.

Strategies currently under consideration for HIV cure are contingent upon first controlling the virus with ART. Therefore, in keeping with current treatment guidelines, the usefulness of a cure intervention will depend upon the engagement and retention of infected persons in clinical care.⁴ An optimistic assumption is that publicity associated with development of a safe and effective cure may drive more infected persons to seek early HIV testing and management. Widespread implementation of HIV cure would then decrease both HIV prevalence and incidence.⁴ The scalability of each HIV cure approach will depend on its effectiveness, but also on its tolerability and affordability. Notably, many current HIV cure ideas involve treatments that are not yet widely used in the clinic.⁵ “Off the shelf” medications that require no further research and development expenditure, and have well established toxicity profiles, are therefore attractive potential options for HIV cure.

The major barrier to HIV eradication is the HIV reservoir. The reservoir consists predominately of memory CD4+ T cells, which harbor non-replicating HIV DNA that is integrated into chromosomal DNA. Complete elimination of these cells, or at least inactivation of the “silent” HIV within these cells, is required for cure. The total reservoir typically consists of approximately 1-10 million CD4+ T cells.⁶⁻⁸ On a per cell basis, the rate of reactivation of HIV is extraordinarily low. Yet, antiretroviral treatment interruption (**ATI**) studies demonstrate that HIV will reactivate approximately once per week.^{9,10} Thus, to achieve a lifetime remission from HIV reactivation off ART, the vast majority of the reservoir must be eliminated.

Two groups estimated that a one-year remission off ART would require a 100- to 1000-fold reduction in the number of latently infected cells.^{10,11} Given the low number of cells that would remain after such an intervention, a major challenge is to achieve reliable and rapid measurement of the HIV reservoir. Total cell-associated HIV DNA is a sensitive method to estimate reservoir size,¹²⁻¹⁵ but is misleading because most HIV DNA is not replication competent. The gold standard quantitative viral outgrowth assay (**QVOA**) is specific for replication competent HIV but is laborious, slow and requires a large number of CD4+ T cells, making it less feasible for repeat monitoring.¹⁶ Much of the reservoir exists within deep tissues such as lymphatic tissue in the gastrointestinal tract (**GALT**) and lymph nodes: this adds to the challenge of quantitating latently HIV infected cells.

Numerous technologies are being evaluated to eradicate the HIV reservoir. A majority of potential interventions are in preclinical development. Examples include gene therapy delivery of HIV DNA editing enzymes, chimeric antigen T cell therapy (CAR T cells), therapeutic vaccines, delivery of HIV

Clinical Protocol

antibodies or anti-HIV synthetic peptides, and transplantation of HIV resistant cells.⁵ Several latency-reversing agents (**LRA**s) are being actively tested in human study participants.¹⁷ LRAs are designed to reactivate HIV from its latent form with the hope of inducing two downstream effects. First, cells with replicating HIV will lyse due to HIV replication while ART prevents infectious spread to new cells. Second, presentation of HIV peptides on the cell surface will induce a cytolytic immune response that may be augmented by other interventions such as a vaccine or CAR T cells. Unfortunately, demonstration of a reservoir reduction following clinical LRA therapy is so far lacking.¹⁷

1.2 Study rationale

Our research group designed a mathematical model with the initial goal of identifying the most important barriers to eradication of the reservoir. This analysis led to the conclusion that anti-proliferative therapy provided over a sustained period of time is potentially a far more potent approach than one time use of LRAs.¹⁸

Based on extensive existing phylogenetic data, we first assumed that after suppressive ART of >1 year, ongoing HIV replication does not contribute to persistence of the HIV reservoir.¹⁹⁻²⁶ We demonstrated that even in the context of partially effective ART, the survival of the latent reservoir can be decoupled from active viral replication. The latent pool of cells can then be characterized with an exponential clearance equation, which is analogous to the compound interest formula in finance and characterizes the slow clearance of the HIV reservoir over many decades. Two papers estimate the reservoir clearance half-life to be 44 months,^{6,7} which means that it would take over 60 years for the reservoir to be cleared with ART alone.

On suppressive ART, the latent reservoir clearance rate consists of the sum of three latent cell processes: proliferation, death and reactivation to active viral replication. Importantly, observed per cell proliferation rates are several orders of magnitude higher than reactivation rates.²⁷ We identified in the literature that cells composing the reservoir, including effector memory (**TEM**), central memory (**Tcm**), naïve (**Tn**) and stem cell like (**Tscm**) memory CD4+ T cells, proliferate at rates similar to comparable cells without HIV integration.^{26,28-30} For example, a **Tcm** cell divides roughly once every 2 months.³¹ On the other hand, ATI studies suggest that a single HIV-infected cell within the reservoir will reactivate at a rate of approximately once every 265 years.¹⁰ Thus, because the viral reactivation rate is negligible and the net clearance rate of the latent reservoir approaches zero,^{6,7} the proliferation and death rates must be approximately in equilibrium.

Using our model, we demonstrate that a small but prolonged decrease in HIV reservoir clearance rate would have a greater impact on decreasing the size of the reservoir than a single larger decrease in reservoir size, as would occur with a single dose of effective LRA treatment. This result is analogous to compound interest whereby small changes are amplified when applied over a long duration. Our model predicts that decades of ART would be needed after a 10-fold one-time reduction in the reservoir to achieve cure. Yet, a continuous 10-fold reduction in clearance rate would induce a functional cure in under five years.

We next examined the theoretical effects of continuous alterations of the component rates that determine the overall clearance rate. If we assume a medical intervention that has a continuous effect on HIV reactivation, this intervention would need to induce a 100-fold increase in the basal reactivation rate for three years in order to approach a functional cure. On the other hand, just a 3-fold decrease in the proliferation of reservoir cells extended over three years of treatment may be enough for a functional cure. Therefore, continuous anti-proliferative therapy would be the most efficient method to induce a cure.

Clinical Protocol

Several pieces of data are consistent with the predictions of our mathematical model. Chapuis *et al* treated six study participants with MMF for 20 weeks.³² Half of these patients demonstrated a substantial reduction in reservoir size measured by QVOA, ranging from 1 to 2 orders of magnitude. In addition, treated patients had a decrease in T cell proliferation as measured by Ki67 staining. Garcia *et al* treated nine chronically infected and ART-suppressed study participants with low-dose MMF for 17 weeks in addition to their ART.³³ The authors noted that serum obtained 12 hours post dosing demonstrated a pronounced anti-proliferative effect (>60% inhibition) on T cells *in vitro* in 6 of the 9 subjects on MMF. These 6 patients had a notable median 6-12 week delay in viral rebound and a lowering of viral load set point following ATI, compared to the untreated controls as well as to the three study participants on MMF whose serum did not have strong anti-proliferative activity. A delay of this magnitude is consistent with an approximately 10-fold decrease in reservoir size,³⁴ which aligns with predictions from our model. Our model further suggests that had participants taken ART and MMF for three years as we propose, then long-term remission would have been possible.

While MMF has been used in HIV+ patients receiving organ and blood transplants, findings under these conditions indicate multiple confounders in transplantation settings,³⁵⁻³⁸ rendering them unsuitable to evaluate the effect of MMF.

1.3 Study drug

Mycophenolate mofetil (MMF) is a prodrug of mycophenolic acid, which inhibits an enzyme required for proliferation of lymphocytes, including B and T cells. MMF is used to prevent organ rejection following lung, liver, heart and kidney organ transplantation. Moreover, MMF is commonly used as a steroid-sparing agent for autoimmune diseases.

MMF safety in HIV-infected patients has been established in over 300 HIV+ solid organ transplant recipients and other clinical settings.³⁹⁻⁵⁹ Fewer than 10% of treated participants developed nausea. Renal toxicity, cytopenia, opportunistic infections or decrease in peripheral CD4+ T cell counts were not noted.^{39-45,49} Of note, we will use 500mg twice daily in our study, which is lower than the 2-3g/day to prevent organ rejection. We will increase to 750 mg twice daily if an adequate anti-proliferative effect is not noted on a lower dose.

Myfortic[©] is an enteric coated version of the MMF which is associated with less nausea, vomiting and diarrhea. Myfortic[©] will be used for participants who have refractory nausea, vomiting and / or diarrhea on MMF, and who wish to remain in the study.

2.0 STUDY HYPOTHESES AND OBJECTIVES

2.1 Hypotheses

- 2.1a MMF or Myfortic[©] will be well tolerated and will not decrease adherence to or antiviral efficacy of ART.
- 2.1b Peripheral CD4+ T-cell counts and percentages will not meaningfully decrease during treatment with MMF or Myfortic[©] and ART.
- 2.1c There will be no excess risk of opportunistic infections in MMF or Myfortic[©] treated study participants.
- 2.1d MMF or Myfortic[©] therapy will lead to a progressive decrease in reservoir size over 22 months of treatment.

Clinical Protocol

- 2.1e MMF or Myfortic[©] therapy will lead to a continual shift in HIV reservoir composition from primarily effector memory CD4+ T-cells (T_{em}) and central memory CD4+ T-cells (T_{cm}), to primarily stem cell like memory (T_{scm}) and naïve (T_n) CD4+ T-cells.
- 2.1f MMF or Myfortic[©] will eliminate detectable measures of the HIV reservoir, including cell-associated DNA/mRNA, and quantitative viral outgrowth.
- 2.1g MMF or Myfortic[©] will not decrease the humoral immune response to routine annual influenza vaccination.

2.2 Primary Outcomes

- 2.2a Change in cell-associated HIV DNA (ca-DNA) reservoir size as measured by multiplexed digital droplet PCR in study participants on versus off MMF or Myfortic[©] (historical controls).
- 2.2b Change in HIV replication by single copy viral load (scVL) in study participants on versus off MMF or Myfortic[©] (historical controls).
- 2.3c Change of viral reactivation by cell-associated HIV mRNA in study participants on versus off MMF or Myfortic[©] (historical controls).
- 2.3d Change of the inducible HIV reservoir size by quantitative viral outgrowth assay (QVOA) in study participants on versus off MMF or Myfortic[©] (historical controls).
- 2.3d Change of the cellular composition of the HIV DNA reservoir in study participants on versus off MMF or Myfortic[©] (historical controls).

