2.3 Secondary Outcomes

- 2.3a CD4+ T cell numbers that recently emigrated from the thymus
- 2.3b Blood CD4+ T cell count
- 2.3c Complete blood cell count, comprehensive metabolic panel
- 2.3d Incidence of opportunistic infection
- 2.3e Antibody response to annual influenza vaccination

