3.0 STUDY DESIGN

This is an open-label, randomized Phase II trial to determine whether MMF given over 22 months meaningfully decreases the size of the HIV reservoir.

At the University of Washington in Seattle, we will enroll 5 study participants who have been on ≥ 2 years of suppressive ART. Study participants will be followed closely for at least 22 months with safety labs and serial measurements of the HIV reservoir (specifically, cell-associated HIV DNA and mRNA (**ca-DNA & ca-RNA**), quantitative viral outgrowth assay (**QVOA**), and single copy plasma viral

Clinical Protocol

load (**scVL**)). A “go/no-go” decision will occur after 12 months based on pre-defined thresholds of reduction in the HIV reservoir measured with ca-DNA.

All participants will be offered enrollment in a sub-study in which an anoscopy with rectum biopsies is performed on 3 occasions to assess the reservoir in the gastrointestinal lymphatic tissue (**GALT**).

We will vaccinate study participants with the annual influenza vaccine and analyze their humoral response to this vaccine approximately one month later with a routine blood draw done in conjunction with a safety labs blood draw.

We hypothesize that low doses of MMF will be well tolerated among healthy HIV-infected study participants who have fully ART-suppressed HIV. We hypothesize that the incidence of opportunistic infections will not exceed that of comparable larger cohorts of HIV-treated patients. Of note, certain opportunistic infections such as herpes zoster or HSV-2 recurrence continue to occur despite suppressive ART, while pneumocystis pneumonia, CMV end organ disease, cryptococcus and many other opportunistic infections are much less common in this context. Therefore, in the event of an infection, we will confer with the data safety management (DSM) panel to discuss whether this event is directly attributable to MMF. Finally, we hypothesize that peripheral blood CD4+ and CD8+ T cell counts will remain unchanged throughout MMF therapy, and that HIV replication will remain controlled on ART with addition of MMF.

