We hypothesize at least a 0.25-log reduction in cell-associated HIV DNA at one-year intervals in study participants who have a demonstrated anti-proliferative response to MMF treatment. We hypothesize that cell-associated HIV DNA will undergo a shift from predominant residence in T_{CM} and T_{EM} to predominant residence in T_N and T_{SCM} . In regards to our sub-study, we predict that reservoir depletion will occur with equivalent rates in blood and GALT.

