8.2 Statistical outcomes

8.2.1 Main statistical outcome

- Change in cell-associated HIV DNA (ca-DNA) reservoir size as measured by multiplexed digital droplet PCR in study participants on versus off MMF (historical controls).

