8.2.2 Secondary statistical outcomes

- Change in HIV replication by single copy viral load (scVL) in study participants on versus off MMF (historical controls).
- Change of viral reactivation by cell-associated HIV mRNA in study participants on versus off MMF (historical controls).
- Change of the inducible HIV reservoir size by quantitative viral outgrowth assay (QVOA) in study participants on versus off MMF (historical controls).
- Change of the cellular composition of the HIV DNA reservoir in study participants on versus off MMF (historical controls).
- CD4+ T cell numbers that recently emigrated from the thymus
- Blood CD4+ T cell count
- Complete blood cell count, comprehensive metabolic panel
- Incidence of opportunistic infection
- Antibody response to annual influenza vaccination

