8.2.3 Rationales of using the main and secondary statistical outcomes for the study

The primary and secondary outcomes were chosen to test our hypotheses that MMF plus ART will reduce the size of the HIV latent reservoir more rapidly than ART alone. Various reservoir assays are used for the secondary outcomes to highlight the fact that each assay has limitations in terms of sensitivity and specificity, as well as blood volume required for the assay. Safety labs and clinical measures such as CD4+ T cell count and HIV plasma RNA are included as secondary outcomes to allow us to assess the safety of the addition of MMF to ART.

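### Section 2.2 names five primary outcomes and Section 8.2 names one, ca-DNA; nothing says which governs, and the analysis and power text do not match ca-DNA

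*Combined protocol and SAP*

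**What the plan says.** Section 2.2, headed as primary outcomes, has five items: ca-DNA, scVL, ca-mRNA, QVOA and cellular composition. Two of them read "2.2b Change in HIV replication by single copy viral load (scVL) in study participants on versus off MMF or Myfortic" and "2.3d Change of the inducible HIV reservoir size by quantitative viral outgrowth assay (QVOA) in study participants on versus off MMF or Myfortic".

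Section 8.2.1 gives one main outcome: "Change in cell-associated HIV DNA (ca-DNA) reservoir size as measured by multiplexed digital droplet PCR in study participants on versus off MMF". Section 8.2.2 lists the other four as secondary in nearly the same words, for example "Change in HIV replication by single copy viral load (scVL) in study participants on versus off MMF (historical controls". Section 8.2.3 adds: "Various reservoir assays are used for the secondary outcomes to highlight the fact that each assay has limitations".

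Section 3.0 leans the same way. Its efficacy hypothesis is "We hypothesize at least a 0.25-log reduction in cell-associated HIV DNA at one-year intervals", and the go/no-go decision is "based on pre-defined thresholds of reduction in the HIV reservoir measured with ca-DNA".

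The Protocol Summary is broader and vaguer. Its Primary Objective has three hypotheses: reservoir size, reservoir composition, and elimination of detectable reservoir by ca-DNA/mRNA and viral outgrowth. Its Endpoint row defines the primary endpoint as the size of the reservoir when drug treatment ends, without an assay.

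**The concern.** With five participants, no concurrent control group (Section 8.3), and no stated alpha or success rule, fixing the primary outcome in advance is one of the few protections against choosing the result after seeing it. Here a report could call scVL, ca-mRNA, QVOA or composition either primary or secondary and cite a section in support. The assays can disagree: Section 1.1 describes total HIV DNA as sensitive but misleading about replication competence, and QVOA as specific for replication-competent virus.

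The statistical text does not settle the matter, because the passages that should put ca-DNA into practice use other measures or none. The endpoint is also a level in the summary but a change in Sections 2.2 and 8.2.

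**Working it through.** **1. Status of each outcome, side by side**

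| Outcome | Section 2.2 | Section 8.2 | Primary Objective (summary) |
|---|---|---|---|
| ca-DNA | primary | main (8.2.1) | hypothesis 3 by name; hypothesis 1 concerns size, no assay |
| scVL | primary | secondary | not named |
| ca-mRNA | primary | secondary | hypothesis 3 |
| QVOA | primary | secondary | hypothesis 3 |
| Composition | primary | secondary | hypothesis 2 |

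The count is five primary outcomes against one; four of the five change status.

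**2. Could misnumbering explain it?** The last three items under 2.2 are labelled 2.3c, 2.3d and 2.3d. This looks like a drafting slip, but it does not resolve the conflict. The scVL item is correctly numbered 2.2b and is still secondary in 8.2.2. Section 2.3 also has its own complete a-to-e list (its item c is "2.3c Complete blood cell count, comprehensive metabolic panel"), and none of the five reservoir outcomes is in it.

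**3. What each operative passage measures**
- Hypothesis and go/no-go in Section 3.0: ca-DNA.
- Summary endpoint: no assay.
- Per-person slope, Section 8.6: log viral load. Section 4.1(d) selects participants with HIV RNA below 40 copies/mL on four occasions.
- Mixed model for reservoir size, Section 8.6: the reservoir, no assay.
- Planning rates and the claim of adequate power, Section 8.4.1: log10 IUPM, the outgrowth scale.

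No passage in 8.4.1 or 8.6 applies the reservoir-size analysis to ca-DNA by name.

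**4. The plan's own figures (Section 8.4.1)**
- Annual fall on ART alone: 12 × 0.0068 = 0.0816 log10, stated as 0.082.
- As a percentage: 1 − 10^(−0.0816) = 17.1%, stated as 17%.
- Annualized SD: 12 × 0.017 = 0.204, stated as 0.2.

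All three reproduce. The arithmetic is sound, but every input is in IUPM, so none of it supports a power statement for ca-DNA.

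**5. Timing.** The summary gives a 22-month treatment duration, so a nominal time exists. Treatment may nevertheless end at month 12 after a no-go (Sections 6.4 and 9.0), at other times for toxicity, pregnancy or virologic failure (6.2, 6.4), or later under the extension in 8.1. No rule says how these cases enter the endpoint. For a no-go, Section 6.1 has the participant leave the study, while Section 6.4 continues follow-up off drug.

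**6. Precision of a fixed-time within-participant change, if one is reported.** Half-width of the 95% interval = t(0.975, 4 df) × SD / √5, with t = 2.776. The documents give no ca-DNA SD, so the IUPM SD is borrowed as an assumption.
- Month 12, SD 0.2: 2.776 × 0.2 / 2.236 = 0.25 log10.
- Month 22, SD 0.017 × 22 = 0.374: 2.776 × 0.374 / 2.236 = 0.46 log10.

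The month-12 half-width is as large as the 0.25-log fall hypothesized at one year.

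**The case against.** The strongest reply is that ca-DNA is plainly intended. Section 8.2.3 calls the other reservoir assays secondary, and both the 0.25-log hypothesis and the go/no-go in Section 3.0 use ca-DNA. For a five-person study that says it does not need adequate power, one clarifying sentence might do. Much of this stands: ca-DNA is the better-supported reading, and the practical harm is limited to reporting. But the Primary Objective broadly matches the longer list in 2.2, so the other reading has support outside that section. A sentence about status would also leave 8.6 and 8.4.1 on other scales.

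A reader might infer four stronger points that the documents do not support.
- **Inflated type I error from five primary tests.** The plan states no alpha and no rule by which any one outcome counts as success, so no family-wise rate can be attributed to it.
- **Large distortion from unequal time on drug.** Section 8.6 analyses slopes. Under a constant log10 rate, early and late stops have the same expected slope. The timing problem belongs to the summary's end-of-treatment level and to the missing rule for off-drug data.
- **No time point at all.** Twenty-two months is given as the nominal duration in the summary and Section 8.1, and hypothesis 2.1d uses it.
- **Viral load is no measure of the reservoir.** Section 3.0 lists scVL among the serial reservoir measurements. The sound objection is narrower: log viral load is not the ca-DNA outcome named in 8.2.1.

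**Conclusion.** The concern holds as a conflict over outcome status that carries into the analysis text. Four of five outcomes are primary in one section and secondary in another, with no statement of precedence. The summary endpoint names no assay and uses a level where 2.2 and 8.2 use a change. Followed literally, the only named outcome for the reservoir-size slope in 8.6 is log viral load, so the main outcome in 8.2.1 would not be analysed.

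This should be corrected before analysis. It casts no doubt on the data collected. The status conflict rests on the text alone and needs no numerical assumption; only the interval half-widths depend on an assumed SD.

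**What to change.** 1. In the summary endpoint and Sections 2.2 and 8.2, name the change (slope) in log10 ca-DNA over the nominal 22-month treatment period as the single primary outcome. Move scVL, ca-mRNA, QVOA and composition to secondary, report them with confidence intervals, and correct the numbering. Align hypotheses 2 and 3 of the Primary Objective with that status; otherwise hypothesis 2 has no primary outcome and hypothesis 3 is only partly covered.
2. In Section 8.6, replace log viral load with log10 ca-DNA, name ca-DNA as the mixed-model outcome for reservoir size, and analyse scVL separately as secondary.
3. In Section 8.4.1, state that the planning rates and the power statement apply to QVOA/IUPM and not to ca-DNA.
4. Reconcile Sections 6.1 and 6.4 on follow-up after a no-go, and state whether off-drug data enter the slope.
5. If a fixed-time within-participant change is also reported, give its horizon and its interval.

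The cost is text changes, with no new visits, blood or assays. Replacing the summary's end-of-treatment level with a slope changes the estimand there, so it is more than wording. The comparison with historical controls needs longitudinal ca-DNA control data, and the documents give only IUPM rates; a within-participant change alone cannot separate MMF from decline on ART. The main scientific cost is that a fall in QVOA alone could no longer be the primary result.
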